### 6.5.4.3 Urinalysis

In this trial, urine dipsticks will be collected at Visits 101, 199, and 299/EOT.

### 6.5.4.4 Hepatotoxicity

Any liver event which meets the criteria for “medically significant” event as outlined in [Table 13-1 of Appendix 7](#) should follow the **standard procedures for SAE reporting** as described in [Section 7.2](#).

## 6.5.5 Electrocardiogram (ECG)

ECGs must be recorded after the patient rests (10 minutes if possible) in the supine position to ensure a stable baseline.

When the ECG recording time coincides with vital signs, spirometry, and blood draws, the ECG should be performed first, followed by vital signs and the blood draws but with enough time planned to ensure the spirometry is performed at the planned time point outlined in [Table 6-2](#) and [6-3](#). Spirometry must be performed as close to the scheduled time point as possible.

### Centralized ECG equipment

At Visit 101, a screening ECG will be measured to test for eligibility for trial inclusion. Patients with an abnormal ECG at Visit 101, due to technical/mechanical faults, may be rescreened.

At Visits 199/201 and 299/End of study, ECGs will be measured at pre-dose (prior to spirometry) and 20 minutes and 50 minutes post-dose of study medication as indicated in **Table 6-2** and **6-3**. All ECGs should include 12 standard leads. An ECG tracing should be taken for those patients who prematurely discontinue from the study treatment.

For each ECG performed original traces and identical duplicate traces should be printed. Each ECG will be sent electronically for central review directly from the ECG machine. Two 'identical' duplicate print-outs will be generated and kept at the investigator site as source documentation and as back-up for submission to the central laboratory in case of problems with the electronic transmission. Each print out will be kept at the investigator site and will be dated and signed. The subject's number, the date, actual time of the tracing, and Study Code must appear on each page of the tracing.

Full details of all procedures relating to the ECG collection and reporting will be contained in an investigator manual to be provided by the central ECG group to each investigator site. In the event that the central cardiologist reports that an ECG is abnormal, the investigator must assess whether the ECG abnormality is clinically significant or not. A clinically significant abnormality should be reported as an AE. If necessary a pediatric cardiologist may be consulted.

Clinically significant ECG findings at baseline must be discussed with the sponsor before administration with investigational treatment.

If a patient experiences a clinically significant change in cardiac rhythm or other clinically significant cardiovascular abnormality, the investigator should consider withdrawing the patient from the study.

Clinically significant abnormalities should be recorded on the relevant Section of the medical history/Current medical conditions/AE CRF/e-CRF page as appropriate.

### **6.5.6 Worsening of asthma**

Investigators and patients will be instructed how to deal with worsening of asthma symptoms. The data captured in the patient diary will also be used to alert the patient and/or investigator to possible signs of worsening asthma. Worsening asthma should be recorded as an Adverse Event. The investigator must provide the patient's parent/ legal guardian with written instructions to contact the investigator if at any time during the trial from the Run-in onwards one or more of the following criteria of worsening asthma develops:

#### **Asthma Worsening Criteria**

- Excessive use of rescue medication (more than 200 µg salbutamol/ 180 µg albuterol four times per day for three consecutive days)
- Decline in PEF from the baseline PEF of  $\geq 20\%$  for one day or  $\geq 15\%$  for 3 consecutive days.
- 20% decrease in FEV1 from baseline value (this criterion applies to Investigator review at the time of a study visit and an alert setting in the Masterscope)
- $< 60\%$  of PEF compared to baseline
- Night time awakenings requiring SABA use on at least 2 out of any 3 consecutive nights (patients may be continued in the study based on their general pattern of night time symptoms as per investigators judgement)

- Urgent unscheduled clinic visit due to asthma related deterioration

**Note:** The baseline FEV1 and PEF for the Run-in epoch would be the FEV1 and PEF taken at Visit 101. The baseline FEV1 for the treatment epoch is the mean of the 45 min and 15 min pre-dose FEV1 measurements at Day 1. The baseline PEF (morning and evening) for the treatment epoch is calculated at visit 199 and is the mean of the best of the three daily PEF measurements over the past 14 days.

If patients develop any of the above criteria, the patient should notify the investigator and be evaluated by the investigator and treated as clinically appropriate.

If any of the above criteria are met while a patient is in the Run-in epoch of the study, they may be withdrawn if, in the opinion the investigator, it is appropriate to do so.

Patients should also be withdrawn for safety reasons if, in the opinion of the investigators, it is appropriate to do so.

Worsening of asthma symptoms may require unscheduled evaluation between visits. Study site personnel must be available to monitor and document patient's progress until asthma control is regained.

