During the trial, additional treatment options for the patients are limited as the protocol does not allow administration of other asthma medications except ICS, previously initiated Leukotriene Receptor Antagonist (LTRA), and short acting  $\beta$ 2-adrenergic receptor agonist (SABA) for rescue use. Furthermore, patients will have to discontinue their pre-study ICS controller medication and begin taking fluticasone propionate. Change of the device and controller medication may introduce a risk for worsening of asthma symptoms and lung function for these patients due to reduced adherence. ICS therapy as controller treatment for asthma is aligned with GINA guidelines at all times. In order to minimize the risk to patients, extensive safety monitoring (e.g. electronic daily patient diary assessment of rescue medication use, PEF measurements, and adverse event monitoring) will be carried out throughout the study. E-Diary data will be transmitted electronically from the device to the investigator regularly.

Investigators should withdraw a patient if they feel, based on their medical judgment, that this would be best for the patient, or after occurrence of any of the discontinuation criteria listed in [Section 5.6.2](#). Parents/legal guardians are also instructed that their child can withdraw from the trial at any time, and for whatever reason.

The potential individual benefit for the patient lies in a thorough medical evaluation of the patient's disease and close clinical monitoring for the duration of the study. The potential benefit also includes an improvement in lung function, and symptoms (during treatment periods). All patients in the study will be receiving active treatment with indacaterol acetate on ICS background, which is consistent with GINA treatment guidelines. There [is no placebo arm](#), which mitigates risk of under-treatment.

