#### **5.5.3.2 Handling of additional treatment**

The following non-study drug will be monitored as follows:

The non-study drug must be received by a designated person at the study site, handled and stored safely and properly, and kept in a secured location to which only the investigator and designees have access. Clinical supplies are to be dispensed only in accordance with the protocol.

The investigator must maintain an accurate record of the shipment and dispensing of the non-study drug in a drug accountability log. Monitoring of drug accountability will be performed by monitors during site visits or remotely and at the completion of the trial. Patients will be asked to return all unused non-study drug and packaging at the end of the Run-in for the Run-in medication and at the end of the study or at the time of discontinuation of study drug for the rescue medication.

These medications are:

- Salbutamol (100 µg) or albuterol (90 µg) used as rescue medication from Visit 1 to Visit 299
- Fluticasone propionate (100 µg b.i.d. or acceptable dose equivalent as outlined in [Section 3.1](#) used as Background medication from Visit 1 to Visit 299

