### 6.5.7 Asthma Exacerbation

**In this trial, any patient who suffers from a moderate or severe asthma exacerbation will be discontinued from this trial.**

Asthma exacerbations will be recorded as Adverse Events.

A **severe asthma** exacerbation (Draft note for guidance on clinical investigation of medicinal products for treatment of asthma CHMP/EWP/2922/01 Rev.1) is defined as an aggravation of asthma symptoms (like shortness of breath, cough, wheezing, or chest tightness) that requires systemic corticosteroids (SCS) for at least three consecutive days and/or a need for an ER visit (or local equivalent structure), or hospitalization due to asthma or death due to asthma.

- Start date and end date:
- In case of the use of SCSs for at least three days, the first day of treatment will determine the onset date of the event while the last day of treatment will define the stop date.
- In the event that an ER visit and/or hospitalization due to asthma exacerbation were not associated with a course of SCSs as described above, start and end dates would be defined by the corresponding dates entered by the Investigator in the CRF.

A **moderate asthma** exacerbation in this protocol is defined as the occurrence of two or more of the following:

1. Progressive increase of at least one of the asthma symptoms like shortness of breath, cough, wheezing, or chest tightness. The symptoms should be outside the patient's usual range of day-to-day asthma and should last at least two consecutive days
2. Increased use of "rescue" inhaled bronchodilators defined by:
  - a. 50% increase in SABA use and >8 puffs on 2 out of any 3 consecutive days compared to baseline captured  
OR
  - b. Night time awakenings requiring SABA use on at least 2 out of any 3 consecutive nights

3. Deterioration in lung function, which last for two days or more but usually not severe enough to warrant SCSs for more than 2 days or hospitalization. This deterioration would be defined by:

- a. 20% decrease in FEV1 from baseline value  
OR
- b. ≥ 20% decrease in am or pm PEF from baseline on 2 out of any 3 consecutive days compared to baseline  
OR
- c. < 60% of PEF compared to baseline

At no time may patients self-medicate (other than rescue medication use) for treatment of asthma exacerbation or worsening of symptoms.

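### One route to a moderate exacerbation in Section 6.5.7 (symptom increase plus heavier SABA use) meets none of the criteria in Section 6.5.6 on which parents are told to call

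*Protocol*

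**What the plan says.** Under Section 6.5.6 the investigator must tell parents in writing "to contact the investigator if at any time during the trial from the Run-in onwards one or more of the following criteria" is met. Six criteria follow:

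- rescue use: "Excessive use of rescue medication (more than 200 µg salbutamol/ 180 µg albuterol four times per day for three consecutive days"
- a PEF fall of at least 20% for one day or at least 15% for three consecutive days
- a 20% fall in FEV1, which is for the investigator to assess at a visit
- PEF below 60% of baseline
- night awakenings needing SABA on at least two of any three consecutive nights
- an urgent unscheduled visit for asthma

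Section 6.5.7 defines a moderate exacerbation as two or more of three components:

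- **Component 1:** "Progressive increase of at least one of the asthma symptoms like shortness of breath, cough, wheezing, or chest tightness", outside the child's usual range and lasting at least two consecutive days.
- **Component 2:** either (2a) "50% increase in SABA use and >8 puffs on 2 out of any 3 consecutive days compared to baseline captured" or (2b) night awakenings needing SABA on at least two of any three consecutive nights.
- **Component 3:** deterioration in lung function, shown by (3a) a 20% fall in FEV1, (3b) a PEF fall of at least 20% on two of any three consecutive days, or (3c) PEF below 60% of baseline.

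The consequence in 6.5.7 is that "any patient who suffers from a moderate or severe asthma exacerbation will be discontinued from this trial". Section 5.6.2 lists the same event as a mandatory treatment stop. It also makes worsening asthma as defined in 6.5.6 a mandatory stop.

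There are two other channels. Section 6.5.6 says "The data captured in the patient diary will also be used to alert the patient and/or investigator to possible signs of worsening asthma", and Section 3.6 says "E-Diary data will be transmitted electronically from the device to the investigator regularly".

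**The concern.** The investigator is bound to stop treatment for a moderate exacerbation and so has to learn of it. During treatment the clinic sees the child on Day 1 and Day 14 only (Table 6-1). In between, the protocol relies on the parent's call and on the diary.

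If an event that requires a stop can occur without meeting any call criterion, a parent who follows the written instructions exactly has no reason to ring. Section 6.5.7 permits rescue medication as self-treatment, so a parent who gives extra SABA for two days and carries on is within the rules.

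The patients are aged 6 to 11. Section 3.6 acknowledges limited indacaterol safety data at this age and relies on close monitoring as mitigation. What is at stake is prompt recognition of a stop event. The primary endpoint is not the issue.

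**Working it through.** No sample size or power figure is involved. The check is whether every route into the 6.5.7 definition also meets a 6.5.6 criterion.

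**Step 1: match each item of 6.5.7 to 6.5.6.**

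| 6.5.7 item | Matching 6.5.6 criterion |
|---|---|
| 1, symptom increase | none |
| 2a, SABA on 2 of any 3 days | none; the rescue item needs 3 consecutive days |
| 2b, night awakenings | the same criterion |
| 3a, FEV1 fall of 20% | FEV1 item, at a visit |
| 3b, PEF fall of at least 20% on 2 of 3 days | PEF fall of at least 20% for one day, which is easier to meet |
| 3c, PEF below 60% | the same criterion |

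**Step 2: count the pairs.** Taking one item from each of two different components:

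- component 1 with component 2: 1 × 2 = 2
- component 1 with component 3: 1 × 3 = 3
- component 2 with component 3: 2 × 3 = 6
- total: 2 + 3 + 6 = 11

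Ten pairs contain 2b or a component 3 item and so meet a 6.5.6 criterion. The remaining pair is 1 with 2a.

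**Step 3: put the two rescue thresholds in the same unit.** Section 5.5.3.2 gives "Salbutamol (100 µg) or albuterol (90 µg) used as rescue medication from Visit 1 to Visit 299". Taking these strengths as per puff:

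- salbutamol: 4 × 200 / 100 = 8 puffs a day
- albuterol: 4 × 180 / 90 = 8 puffs a day

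Read as a daily total, the 6.5.6 item is more than 8 puffs a day, the same count as 2a. The two then differ in persistence (three consecutive days against two of any three) and in the 50% rise that 2a also requires.

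**Step 4: run through three-day patterns.** With H for a day above 8 puffs and L for any other day, 2a can be met by HHL, HLH, LHH or HHH. Assume component 1 is present, with no qualifying night awakenings, no qualifying PEF or FEV1 fall and no urgent visit. Then HHH meets the 6.5.6 rescue item on the third day, while HHL, HLH and LHH meet no 6.5.6 criterion. An enumeration of all three-day combinations of rescue use, night awakenings, PEF, symptoms and FEV1 found no other missed route.

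**Step 5: worked example.** Baseline is 4 puffs a day, followed by 10, 10 and 4. Wheeze worsens progressively beyond the usual range on the first two days. There are no night awakenings, and PEF is down 10%.

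- 2a: (10 − 4) / 4 = 150% rise and 10 > 8 on two of three days, so it is met.
- Component 1: met. Two components make a moderate exacerbation.
- 6.5.6: the third day is 4 puffs, so the rescue item fails. A 10% PEF fall is below both 15% and 20%, and PEF stands at 90% of baseline. No criterion is met.

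**Step 6: the literal reading of the rescue item.** If it means more than 200 µg on each of four occasions, that is at least 3 puffs × 4 = 12 puffs a day. A child using 9, 10 or 11 puffs every day then never meets it. All three counts exceed 8, and for a baseline of 6 puffs or fewer even 9 puffs is a 50% rise (6 × 1.5 = 9), so 2a is met. On this reading the gap no longer closes on day 3.

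**The case against.** The strongest case on the other side is that nothing here is contradictory. Worsening and exacerbation are separate definitions with separate purposes, and the protocol never says that the first must catch every instance of the second.

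Other channels exist as well. Section 6.5.6 opens with a general instruction on handling worsening symptoms. Its diary alert covers possible signs, which may be wider than the list. Section 3.6 describes daily diary assessment and regular transmission, and unscheduled evaluation is provided for. Alert thresholds often sit in device configuration documents that are not to hand.

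The uncovered state is also narrow. On the daily-total reading, two heavy days followed by a third trigger the call, and otherwise rescue use has already fallen. Finally, one pair in eleven is not a frequency, and the three pairs that use 3a are caught by the investigator at a visit, not by a parent's call.

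Much of this stands. The pair count describes coverage and says nothing about how often the route occurs, and the diary is a real partial safeguard. But none of these channels states a trigger for this route. The only criteria the protocol gives for worsening asthma are the ones that omit it. Regular transmission has no stated review interval or action rule, and the urgent-visit item presupposes that the family has already sought care. That rescue use may fall again on day 3 does not help either: Section 6.5.7 still classes the episode as a moderate exacerbation and requires a stop.

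**Conclusion.** The concern holds. Exactly one of the 11 two-component routes to a moderate exacerbation, component 1 with 2a, can occur without meeting any 6.5.6 criterion. On the daily-total reading this happens when more than 8 puffs are used on exactly two of three days. On the literal reading it can also happen with 9 to 11 puffs every day.

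The consequence is possible late recognition of a mandatory stop in a child. Non-detection is not certain. In the worst case, if neither a diary alert nor ad hoc review picks it up, an event complete on Day 2 would wait until Visit 299 on Day 14, which is 14 − 2 = 12 days.

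The puff conversion assumes that the stated inhaler strengths are per puff. The pair logic does not depend on it. How often the route occurs, and whether the configured diary alert would catch it, cannot be determined from the protocol. The point should be corrected, but it does not bear on the primary analysis.

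**What to change.** Add one trigger to the parent-contact instruction in Section 6.5.6 and to the e-Diary alert: any combination that meets the 6.5.7 definition of a moderate exacerbation or, more narrowly, component 1 together with 2a. For parents this can be put simply as worse daytime symptoms for two days together with clearly more reliever use. The device can apply the exact rule, since Appendix 4 shows that the diary already records evening shortness of breath, wheeze, cough and chest tightness, and puffs morning and evening.

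Do not add component 1 or 2a to 6.5.6 as a stand-alone worsening criterion. Setting the rescue item equal to 2a would close the gap, but through Section 5.6.2 two heavy-rescue days alone would then force discontinuation. If either component is used alone to prompt a call, state that it is for contact and evaluation only and is not worsening asthma for the purposes of 5.6.2.

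It would also help to say whether the 6.5.6 rescue item is a daily total or a per-occasion threshold.

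The cost is amendment wording, one line on the parent instruction sheet, one alert setting and a few extra calls to sites. No discontinuation criterion is added, because the combination is already a mandatory stop.

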### 6.5.7 Asthma Exacerbation

**In this trial, any patient who suffers from a moderate or severe asthma exacerbation will be discontinued from this trial.**

Asthma exacerbations will be recorded as Adverse Events.

A **severe asthma** exacerbation (Draft note for guidance on clinical investigation of medicinal products for treatment of asthma CHMP/EWP/2922/01 Rev.1) is defined as an aggravation of asthma symptoms (like shortness of breath, cough, wheezing, or chest tightness) that requires systemic corticosteroids (SCS) for at least three consecutive days and/or a need for an ER visit (or local equivalent structure), or hospitalization due to asthma or death due to asthma.

- Start date and end date:
- In case of the use of SCSs for at least three days, the first day of treatment will determine the onset date of the event while the last day of treatment will define the stop date.
- In the event that an ER visit and/or hospitalization due to asthma exacerbation were not associated with a course of SCSs as described above, start and end dates would be defined by the corresponding dates entered by the Investigator in the CRF.

A **moderate asthma** exacerbation in this protocol is defined as the occurrence of two or more of the following:

1. Progressive increase of at least one of the asthma symptoms like shortness of breath, cough, wheezing, or chest tightness. The symptoms should be outside the patient's usual range of day-to-day asthma and should last at least two consecutive days
2. Increased use of "rescue" inhaled bronchodilators defined by:
  - a. 50% increase in SABA use and >8 puffs on 2 out of any 3 consecutive days compared to baseline captured  
OR
  - b. Night time awakenings requiring SABA use on at least 2 out of any 3 consecutive nights

3. Deterioration in lung function, which last for two days or more but usually not severe enough to warrant SCSs for more than 2 days or hospitalization. This deterioration would be defined by:

- a. 20% decrease in FEV1 from baseline value  
OR
- b. ≥ 20% decrease in am or pm PEF from baseline on 2 out of any 3 consecutive days compared to baseline  
OR
- c. < 60% of PEF compared to baseline

At no time may patients self-medicate (other than rescue medication use) for treatment of asthma exacerbation or worsening of symptoms.

### **6.5.8 Pregnancy and assessments of fertility**

Girls who begin menstruating (reached menarche) will have urine pregnancy tests at study visits 1, 101, 199, and 299/EOT. A positive pregnancy test will result in study discontinuation. Refer to [Sections 5.6.2](#) and [7.5](#) for more details.

### **6.5.9 Appropriateness of safety measurements**

The safety assessments selected are standard for this indication/patient population.

## **6.6 Other assessments**

### **6.6.1 Pharmacokinetics**

Blood samples for PK analysis will be collected in all patients at the following time points below, with the aim to collect indacaterol exposure data in asthma patients.

#### Visit 199/201 (End of Run-in/Randomization)

- Pre-dose: ≤ 2 hours Post-dose: 15 minutes and 1 hour

#### Visit 299/End of treatment

- Pre-dose: ≤ 2 hours
- Post-dose: 15 minutes and 1 hour

All blood samples will be taken by either direct venipuncture or indwelling cannula inserted in a forearm or vein at time points specified in [Table 6-2](#) and [Table 6-3](#).

All time points listed are relative to the time of dose administration. The time of the dosing, as well as actual sample collection date and time will be entered on the PK blood collection summary page of the e-CRF. Sampling problems will be noted in the Notes field of the e-CRF. Details of the blood collection methods and the analytical methods will be provided in the Laboratory Manual.

